8.4.2 VERY GOOD PARTIAL RESPONSE

A response criteria exclusive for Waldenstrom's macroglobulinemia patients, Very Good Partial Response (VGPR) is defined as reduction of Monoclonal IgM protein greater than 90 % from baseline. The spleen and/or liver, if considered enlarged before therapy, on the basis of physical exam or CT scan, should not be palpable on physical examination and should be considered normal size by imaging studies, and nodules related to WM should disappear. (Owen et al 2013)

8.4.3 PARTIAL RESPONSE

Partial response (PR) is defined as the regression of measurable disease and no new sites of disease. Regression is defined as greater than or equal to 50% decrease in the sum of the products of the diameters (SPD) of the index lesions, coupled with no unequivocal increase in size of other lymph nodes, liver or spleen. No new sites of disease should be observed. If bone marrow was involved prior to therapy and a clinical CR was achieved but no bone marrow assessment is completed after treatment, then these patients are considered partial responders (Cheson et al., 2014 Lugano Classification).

For Waldenstrom's macroglobulinemia patients, partial response is defined as reduction of Monoclonal IgM protein between 50-90 % from baseline with regression of measurable disease. Regression is defined as greater than or equal to 50% decrease in the sum of the products of the

diameters (SPD) of the index lesions, coupled with no unequivocal increase in size of other lymph nodes, liver or spleen. No new sites of disease should be observed. (Owen et al 2013)

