8.4 DEFINITIONS OF TUMOR RESPONSE AND PROGRESSION

Evaluable for objective response. Only those patients who have had a pre-treatment baseline efficacy evaluation and at least one post-treatment efficacy evaluation will be considered evaluable for response. These patients will have their response classified according to the definitions stated below.

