8.4.4 MINOR RESPONSE

A response criteria exclusive for Waldenstrom's macroglobulinemia patients, Minor Response (MR) is defined as presence of detectable Monoclonal IgM protein with reduction of monoclonal IgM protein greater than 25 % but less than 50 % from baseline. No new sites of disease should be observed. (Owen et al 2013)

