8.4.5 STABLE DISEASE

Stable disease is defined as the failure to attain CR/PR but does not fulfill the criteria for progressive disease. For those with disease evaluated by CT only, there must be no unequivocal change in the size of the previous lesions on the post-treatment CT scan (Cheson et al., 2014 Lugano Classification)

For Waldenstrom's macroglobulinemia patients, stable disease is defined as presence of detectable Monoclonal IgM protein with less than 25% reduction and less than 25% increase in serum IgM level from baseline. No unequivocal increase in size of other lymph nodes, liver or spleen. No new sites of disease should be observed. (Owen et al 2013)

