8.6 EVALUATION OF BEST OVERALL RESPONSE

The best overall response is the best response recorded from the start of the treatment until disease progression/recurrence (taking as reference for progressive disease the smallest measurements recorded since the treatment started). The patient's best response assignment will depend on the achievement of both measurement and confirmation criteria as per the NHL established criteria used in this study (See Appendix A).

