Complete response (CR)	Absence of serum monoclonal IgM protein by immunofixation. Normal serum IgM level. Complete resolution of extramedullary disease, i.e., lymphadenopathy and splenomegaly if present at baseline. Morphologically normal bone marrow aspirate and trephine biopsy
Very good partial response (VGPR)	Monoclonal IgM protein is detectable $\geq 90\%$ reduction in serum IgM level from baseline Complete resolution of extramedullary disease, i.e., lymphadenopathy/splenomegaly if present at baseline. No new signs or symptoms of active disease
Partial response (PR)	Monoclonal IgM protein is detectable $\geq 50\%$ but $< 90\%$ reduction in serum IgM level from baseline. Reduction in extramedullary disease, i.e., lymphadenopathy/splenomegaly if present at baseline. No new signs or symptoms of active disease
Minor response (MR)	Monoclonal IgM protein is detectable $\geq 25\%$ but $< 50\%$ reduction in serum IgM level from baseline No new signs or symptoms of active disease
Stable disease	Monoclonal IgM protein is detectable $< 25\%$ reduction and $< 25\%$ increase in serum IgM level from baseline No progression in extramedullary disease, i.e., lymphadenopathy/splenomegaly No new signs or symptoms of active disease
Progressive disease	$\geq 25\%$ increase in serum IgM level* [†] from lowest nadir (requires confirmation) and/or progression in clinical features attributable the disease

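### Section 8.4.3 and Appendix A define partial response in Waldenström's differently, so a nodal patient with a deeper IgM fall can be scored a non-responder while a shallower fall counts

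*Combined protocol and SAP*

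**What the plan says.** - **WM partial response (PR), section 8.4.3.** "partial response is defined as reduction of Monoclonal IgM protein between 50-90 % from baseline with regression of measurable disease". The next sentence of the same WM paragraph sets regression at an SPD decrease of 50% or more in the index lesions.
- **WM PR, Appendix A (IWWM-6 table).** IgM down by at least 50% but less than 90%, plus "Reduction in extramedullary disease, i.e., lymphadenopathy/splenomegaly if present at baseline". No percentage is attached.
- **Very good partial response (VGPR), section 8.4.2.** "reduction of Monoclonal IgM protein greater than 90 % from baseline", with nodules gone. Appendix A uses 90% or more.
- **Minor response (MR), section 8.4.4.** "reduction of monoclonal IgM protein greater than 25 % but less than 50 % from baseline", with no new sites and no node-shrinkage condition. Appendix A starts at 25% inclusive.
- **WM stable disease (SD), section 8.4.5.** "less than 25% reduction and less than 25% increase in serum IgM level from baseline".
- **Which text governs.** Section 8.4 says "These patients will have their response classified according to the definitions stated below". Section 8.6 instead ties best response to "confirmation criteria as per the NHL established criteria used in this study (See Appendix A". Sections 8 and 8.3 name the Lugano and IWWM-6 criteria by histology without choosing between the two renderings. Section 9.8, in its sentence on progression, sends the WM criteria to Appendix B, which is the contraception appendix.
- **Use.** Section 9.10.1 makes ORR the primary outcome and counts CR, VGPR, PR and MR for WM. Duration of response (DOR) is in the primary objective (section 2.1) and starts at the first documented response (section 2.2).

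**The concern.** Inclusion criterion 3 requires a measurable lesion and exempts only WM without nodal involvement. The 50% SPD condition therefore reaches every nodal WM patient.

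Under section 8.4, MR stops at a 50% IgM fall and PR begins there, but PR adds a demanding nodal condition that MR lacks. A patient who crosses the 50% IgM line before the nodes have halved drops out of MR without entering PR. The deeper IgM response is then scored below the shallower one.

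Appendix A largely avoids this because it sets no size for the nodal reduction. With both texts in force, the same measurements can give two different WM response rates. A choice made after the data are seen would be a choice about the primary result.

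**Working it through.** The plan gives no figure that depends on this definition, so there is nothing to reproduce. The check applies both sets of rules to the same patients.

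**Inputs.** Section 8.4 rules from 8.4.1 to 8.4.6; Appendix A rules from its WM table; up to 20 WM patients and up to 20 marginal zone patients (synopsis); assessment every 3 cycles of 28 days, and a study that may end after 6 months of treatment (synopsis).

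**Assumptions.** Nodal WM, residual nodes, IgM still detectable, no new sites. Appendix A's unquantified reduction is read as any SPD fall above 0%. The 50-90% range in 8.4.3 is read as including its ends.

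**Step 1: a single assessment.**

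| IgM fall | SPD fall | Section 8.4 | Appendix A |
|---|---|---|---|
| 30% | 30% | MR | MR |
| 50%, 60%, 75% or 89% | 30% or 49% | no WM class | PR |
| 60% | 50% | PR | PR |
| 60% | 0% | no WM class | no class |
| 95% | 50% | no WM class | no class |
| 25% exactly | 30% | no WM class | MR |

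For 60%/30% under section 8.4:
- not CR, because IgM is detectable;
- not VGPR, because 60 is not above 90;
- not PR, because 30 is below 50 on SPD;
- not MR, because 60 is not below 50;
- not WM SD, because 60 is not below 25;
- not progression, because nothing has increased.

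The two texts conflict on PR where IgM falls by at least 50% but less than 90% and SPD falls by more than 0% but less than 50%. An exact 90% IgM fall with all nodes resolved is PR under 8.4 and VGPR under Appendix A. That does not affect ORR.

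**Step 2: best overall response.** Section 8.6 takes the "best response recorded from the start of the treatment until disease progression/recurrence", so another qualifying assessment before progression can rescue a patient.

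| First, then second assessment (IgM/SPD fall, %) | Section 8.4 | Appendix A | Effect |
|---|---|---|---|
| 30/10, then 60/30 | MR | PR | PR rate only |
| 55/20, then 65/40 | no response | PR | ORR changes |
| 20/10, then 60/30 | SD | PR | ORR changes |
| 55/30, then 65/55 | PR at the second | PR at the first | DOR start moves |
| 55/0, then 65/0 | no response | no response | none |

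Six months is about 182 / 28 = 6.5 cycles, which gives 2 scheduled assessments at one per 3 cycles. That is the minimum; patients treated for longer have more. The shift in DOR start is 3 x 28 = 84 days nominally. With a window of 7 days either side at each assessment it is 84 - 14 = 70 to 84 + 14 = 98 days.

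**Step 3: size.** One changed patient moves WM ORR by 1/20 = 5 points, by 1/10 = 10 points if only 10 WM patients are analysed, and combined ORR by 1/40 = 2.5 points. As an illustration, assume 8 of 20 WM responders under section 8.4. Exact 95% limits are the 2.5% quantile of Beta(x, n - x + 1) and the 97.5% quantile of Beta(x + 1, n - x).

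| Reclassified | Responders | ORR | Exact 95% CI |
|---|---|---|---|
| 0 | 8/20 | 40% | 19.1-63.9% |
| 1 | 9/20 | 45% | 23.1-68.5% |
| 2 | 10/20 | 50% | 27.2-72.8% |

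**The case against.** The strongest counter-argument is that the texts need not conflict. Both present themselves as IWWM-6, so 8.4.3 could be putting a number on a term that Appendix A leaves open. The general SD sentence in 8.4.5, or the unknown category in 9.8, gives every patient a place. Section 9 defers derivations to a formal SAP that must be final before database lock. The study is single-arm with no formal claims, the number affected may be zero, and the illustrative intervals overlap heavily.

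Several of these points stand. The reading of reduction as any fall above 0% is an assumption, and every PR assigned under Appendix A in the working depends on it. The 84 days is nominal, and two assessments is a minimum. The inversion is not wholly due to the SPD rule. The 50% ceiling on MR is in both texts, so a patient with no nodal shrinkage, or with IgM down more than 90% and nodes not resolved, has no class under either. Adopting Appendix A narrows the gap but does not close it.

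The rest does not remove the problem. Reading the 50% figure into Appendix A would confirm the inversion. SD and unknown are both non-response, so the effect on ORR is unchanged. Deferral to a later SAP does not settle two contradictory rules already stated. Sections 8 and 8.3 name the IWWM-6 criteria that the Appendix A table sets out, which favours letting that table govern.

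**Conclusion.** The concern holds. The WM PR definitions in 8.4.3 and Appendix A differ, the plan does not settle which governs, and under 8.4 a nodal WM patient with the larger IgM fall can be a non-responder while one with the smaller fall counts in the primary ORR.

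The contradiction is certain, but its effect on the result is not. It is 5 points of WM ORR for each patient whose responder status changes at n = 20. Other patients would change only the PR rate or the start of DOR. The comparison assumes detectable IgM, no new sites and any-fall reading of Appendix A. It should be fixed because it sits in the primary endpoint and the remedy is cheap.

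**What to change.** Before database lock, in the protocol and the formal SAP:

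1. State that the Appendix A WM table governs WM response categories for ORR and for the start of DOR.
2. Remove the 50% SPD requirement from the WM paragraph of 8.4.3, and align the other WM wording and cut-offs in 8.4.2 to 8.4.5 with the table (VGPR above 90% against 90% or more; MR above 25% against 25% or more).
3. Apply the extramedullary condition only when such disease was present at baseline, and say what counts as a reduction.
4. Add, flagged as an addition to the table, how to class a patient who meets the IgM cut-off but fails the extramedullary condition. One option is the best category whose other conditions are met, reading the IgM cut-offs as minimums.
5. Correct the section 9.8 pointer from Appendix B to Appendix A.
6. Reconcile section 8.4.6 with Appendix A on IgM progression. They differ on the cut-off (more than 25% against 25% or more) and on whether confirmation is needed. This also bears on when DOR ends. No rule is proposed here.

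The cost is small. The response changes are wording only and need no new visit or test.

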8.4.4 MINOR RESPONSE

A response criteria exclusive for Waldenstrom's macroglobulinemia patients, Minor Response (MR) is defined as presence of detectable Monoclonal IgM protein with reduction of monoclonal IgM protein greater than 25 % but less than 50 % from baseline. No new sites of disease should be observed. (Owen et al 2013)

8.4.5 STABLE DISEASE

Stable disease is defined as the failure to attain CR/PR but does not fulfill the criteria for progressive disease. For those with disease evaluated by CT only, there must be no unequivocal change in the size of the previous lesions on the post-treatment CT scan (Cheson et al., 2014 Lugano Classification)

For Waldenstrom's macroglobulinemia patients, stable disease is defined as presence of detectable Monoclonal IgM protein with less than 25% reduction and less than 25% increase in serum IgM level from baseline. No unequivocal increase in size of other lymph nodes, liver or spleen. No new sites of disease should be observed. (Owen et al 2013)

8.4.6 RELAPSED DISEASE OR PROGRESSION OF DISEASE

Any of the following conditions will constitute relapsed or progressive disease:

Appearance of any new lesion more than 1.5 cm in any axis, even if other lesions are decreasing in size will be considered relapsed or progressive disease. Increase in FDG uptake in a previously unaffected site should be confirmed with other modalities, a therapeutic decision should not be made solely on the basis of PET without histologic confirmation (Cheson et al., 2014 Lugano Classification).

There is at least a 50% increase from nadir in one of the following:

- The SPD of index lesions,
- The greatest transverse diameter (GTD) of any individual previously involved node, or
- The GTD of any previously involved node provided that the GTD of that node is now ≥ 1.5 cm. (Cheson et al., 2014 Lugano Classification).

For Waldenstrom's macroglobulinemia patients, progressive disease is defined as more than 25% increase in serum IgM level from lowest nadir and/or progression in clinical features attributable to the disease. (Owen et al 2013)

8.5 DEFINITIONS OF DISEASE PARAMETERS

Measurable disease: Measurable lesions are defined as those that can be accurately measured in at least two dimensions with conventional techniques (CT, PET/CT, MRI, x-ray) and meet one of the following criteria: nodal lesion with a long axis > 1.5 cm regardless of short axis, nodal lesion with

long and short axes ≥ 1.0 cm, or extra-nodal lesions with long and short axes ≥ 1.0 cm with spiral CT scan. All tumor measurements should be recorded in centimeters.

Non-measurable disease (evaluable disease): All other lesions (or sites of disease) including small lesions, (< 1.0 cm using spiral CT scan) are considered non-measurable disease. Bone lesions, leptomeningeal disease, ascites, pleural/pericardial effusions, lymphangitis, and cystic lesions are all non-measurable.

Index lesions: All measurable lesions up to a maximum of 6 nodal and extra-nodal lesions total, representative of all involved organs, should be identified as **index lesions** and recorded and measured at baseline. For patients with splenic marginal zone lymphoma without lymphadenopathy, the spleen size should be used as an index lesion. Index lesions should be selected on the basis of their size (clearly measurable in two perpendicular dimensions) and their suitability for accurate repeated measurements (either by imaging techniques or clinically). A baseline sum of product of the diameters (SPD) for all index lesions will be calculated and reported as the baseline SPD. The baseline SPD will be used as reference to further characterize any objective tumor regression in the measurable dimension of the disease.

Non-index lesions: All other lesions (or sites of disease) including any measurable lesions over and above the 6 index lesions should be identified as **non-index lesions** and should also be recorded at baseline. Measurements of these lesions are not required, but the presence, absence, or in rare cases unequivocal progression of each should be noted throughout follow-up.

8.6 EVALUATION OF BEST OVERALL RESPONSE

The best overall response is the best response recorded from the start of the treatment until disease progression/recurrence (taking as reference for progressive disease the smallest measurements recorded since the treatment started). The patient's best response assignment will depend on the achievement of both measurement and confirmation criteria as per the NHL established criteria used in this study (See Appendix A).

8.6.1 DURATION OF RESPONSE

Duration of response is defined as the time from documentation of a response to treatment to the first documentation of tumor progression or death due to any cause, whichever comes first. Duration of the response will be summarized using n (sample size), mean, standard deviation, median, minimum, and maximum for the responders.

Duration of stable disease:

Stable disease is measured from the start of the treatment (Cycle 1/Day1) until the criteria for progression are met.

Progression-Free Survival:

Progression free survival (PFS) is defined as the time from Cycle 1/Day1 to the first documentation of tumor progression or death due to any cause, whichever comes first. This variable will be analyzed via Kaplan-Meier methodology. The median PFS will be estimated.

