	
 • To evaluate the overall response rate (CR + PR + VGPR + MR) and duration of response of TGR-1202 in patients with relapsed or refractory non-follicular indolent non-Hodgkin's lymphoma. 
KEY SECONDARY OBJECTIVES
 
 • To determine the progression free survival of TGR-1202 in patients with relapsed or refractory non-follicular indolent non-Hodgkin's lymphoma • To evaluate Time to Treatment Failure with TGR-1202 • To evaluate the safety profile of TGR-1202 
[REDACTED]
 
[REDACTED]
 
[REDACTED]

Inclusion Criteria	
Patients must meet all of the following inclusion criteria to be eligible for participation in this study:
 
 1. Histologically confirmed diagnosis of B-cell non-follicular indolent non-Hodgkin's Lymphoma meeting at least one of the two following requirements: 
 a. World Health Organization 2008 classification criteria warranting therapy as per investigator discretion for histologies limited to splenic marginal zone lymphoma (SMZL), nodal marginal zone lymphoma (NMZL), or extra-nodal marginal zone lymphoma (ENMZL), and lymphoplasmacytic lymphoma. b. Presence of CD20⁺ lymphoplasmacytic lymphoma involving the bone marrow, positive serum immunofixation for monoclonal IgM and at least one criteria for initiation of treatment as per Consensus panel of International Workshops on Waldenstrom's macroglobulinemia. 2. Relapsed or refractory after at least one prior treatment regimen, with no limit on prior therapies. 3. At least 1 measurable disease lesion >1.5 cm in at least one diameter by CT/CT-PET or magnetic resonance imaging (MRI) in an area of no prior radiation therapy, or in an area that was previously irradiated that has documented progression. 
 a. Exception included for Waldenstrom's macroglobulinemia patients without nodal involvement. 4. Waldenstrom's macroglobulinemia patients must have measurable quantitative IgM monoclonal protein greater than normal value. 5. Adequate organ system function, defined as follows: 
 a. Absolute neutrophil count (ANC) > 1,000 / platelet count > 50,000. b. Total bilirubin ≤1.5 times the upper limit of normal (ULN) c. Alanine aminotransferase (ALT) and aspartate aminotransferase (AST) ≤2.5 x ULN if no liver involvement or ≤5 x the ULN if known liver involvement

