	
indolent non-Hodgkin's lymphoma that is relapsed or refractory following at least one prior standard therapy regimen, without limit on prior therapies.
 
Enrollment
 
Following Screening, qualified patients will be administered TGR-1202 (umbralisib) monotherapy at 800 mg QD.
 
During the study period, all patients will be evaluated for response by CT, PET-CT and/or MRI every 3 cycles. For patients with WM without nodal involvement, response will be assessed by quantitative monoclonal IgM protein every 3 cycles. The best clinical response as well as disease progression will be determined by local investigator. Patients will remain on study treatment until the occurrence of definitive disease progression, unacceptable toxicity, or withdrawal from the study due to investigator decision or other reasons. Patients who discontinue from study treatment (either for toxicity or physician choice) and have not progressed will continue to be followed for progression. All enrolled subjects will be treated for at least 6 months, after which time the study may end.

Dosing Regimen (Cycle = 28 days)
	
TGR-1202 (umbralisib):
 
 • TGR-1202: Orally (800 mg) daily starting on Day 1 of Cycle 1.

Study Drugs
	
TGR-1202 is a highly specific and orally available PI3K delta (δ) inhibitor available in 200 mg tablets, supplied by TG Therapeutics, Inc.

Statistical Considerations
	
Sample Size: Up to 20 MZL patients and up to 20 WM patients may be enrolled in the study. The safety population will include all patients who take at least one dose of study medication. The safety analysis will be based on the safety population. The mITT (modified Intent to Treat) population will include all safety patients who have provided at least some post-baseline efficacy measures. The efficacy assessments will be based on the mITT population.
 
In general, the safety and efficacy data will be presented by histology type (MZL and WM) as well as combined.

LIST OF ABBREVIATIONS AND DEFINITIONS OF TERMS

Abbreviations and Definitions of Terms	
AE	Adverse Event
ALC	Absolute lymphocyte count
ALT	Alanine aminotransferase
AST	Aspartate aminotransferase
AUC	Area Under the Curve
BM	Bone Marrow
Ca	Calcium
CBC	Complete Blood Cell Count
Cl	Clearance
CLL	Chronic Lymphocytic Leukemia
cm	centimeter
Cmax	Maximum Concentration
CR	Complete Response
eCRF	Electronic Case Report Form
CRO	Contract Research Organization

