2 OBJECTIVES AND ENDPOINTS

2.1 STUDY OBJECTIVES

PRIMARY OBJECTIVES

- To evaluate the overall response rate (CR + PR + VGPR + MR) and duration of response for TGR-1202 in patients with relapsed or refractory non-follicular indolent non-Hodgkin's lymphoma.

SECONDARY OBJECTIVES

- To determine the progression free survival of TGR-1202 in patients with relapsed or refractory non-follicular indolent non-Hodgkin's lymphoma.
- To evaluate time to treatment failure with TGR-1202.
- To evaluate the safety profile of TGR-1202

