9.1 SAMPLE SIZE AND POWER

9.2 GENERAL ANALYSIS CONVENTION

Unless otherwise stated, all analyses will be performed using SAS Version 9.2 or higher and all hypothesis tests will be conducted at a two-sided significance level of 0.05.

Summary tabulations will display the number of observations, mean, standard deviation, median, minimum, maximum, and appropriate percentiles for continuous variables, and the number and percentage by category for categorical data. Summaries will present data by treatment arm and overall, if appropriate. The data listings will include all available efficacy and safety data.

In general, safety and efficacy data will be presented by histology type and overall.

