9.9 MISSING VALUE HANDLING PROCEDURES

In general, other than for partial dates, missing data will not be imputed and will be treated as missing. The algorithms for imputation of partial dates vary depending upon the parameter and are presented in the Statistical Analysis Plan.

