9.10 STATISTICAL ANALYSES

9.10.1 PRIMARY EFFICACY VARIABLE

The primary efficacy outcome is Overall Response Rate (ORR). The ORR is defined as percent of patients who achieve CR or PR for MZL histology type patients and is defined as percent of patients

who achieve CR, VGPR, PR or MR for WM histology type patients. The estimated response rates as well as the two-sided 95% confidence interval of the response rate will be presented.

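### Section 8.6.1 summarises duration of response with a raw mean and median and no censoring, which understates it when responses are ongoing at cut-off

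*Combined protocol and SAP*

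**What the plan says.** Section 8.6.1 defines DOR as running from documented response to progression or death, then prescribes: "Duration of the response will be summarized using n (sample size), mean, standard deviation, median, minimum, and maximum for the responders". It does not say how a response that has not ended is entered. For PFS, later in the same section and with the same end events, it says: "This variable will be analyzed via Kaplan-Meier methodology".

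The statistics listed for DOR are essentially those that Section 9.2 sets for any continuous measure: "Summary tabulations will display the number of observations, mean, standard deviation, median, minimum, maximum, and appropriate percentiles for continuous variables". Section 9.9 adds: "In general, other than for partial dates, missing data will not be imputed and will be treated as missing". Section 9.10.2 lists DOR among the secondary variables and leaves their analysis to judgement. Section 9 promises a later SAP that will cover, among other things, censoring of time-to-event variables. No such rule appears in the documents provided.

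On follow-up, the synopsis (Study Design) states: "All enrolled subjects will be treated for at least 6 months, after which time the study may end". On status, the primary objective in the synopsis reads: "To evaluate the overall response rate (CR + PR + VGPR + MR) and duration of response of TGR-1202", and Section 2.1 agrees, whereas Section 9.10.1 names ORR alone as the primary outcome.

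**The concern.** A responder who has neither progressed nor died at cut-off has a DOR known only to exceed the time observed so far. A raw mean, SD and median cannot represent that. Whoever programs the table must choose between two ways of following the text:

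1. **Counted:** the time to cut-off is entered as if the response had ended.
2. **Dropped:** with no end date, DOR is treated as missing under Section 9.9, and only completed responses are summarised.

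Both push the result down, by an amount that depends on when the study stops rather than on the drug. At stake is a misleadingly short DOR for an endpoint named in the primary objective.

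**Working it through.** The plan has no DOR target or sample-size calculation to reproduce, so the check has three parts: direction, a hand calculation, and a simulation. T is the true DOR with distribution F; C is the time from response to cut-off.

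**1. Direction**

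- *Counted.* Each entry is min(T, C) ≤ T, strictly smaller for every ongoing response. The raw mean is therefore below the same patients' eventual mean once one response is ongoing. The raw median is lower or unchanged, never higher.
- *Dropped.* With C independent of T, P(T > t | T ≤ C) = E[(F(C) − F(t))⁺] / E[F(C)] ≤ 1 − F(t). Completed responses are shorter in distribution, so the expected mean and median are low. A single data set can go the other way: completed durations of 10 and 12 months, plus a response ongoing at 1 month that ends at 3, give a completed-only mean of 11.0 against an eventual (10 + 12 + 3)/3 = 8.3. Counting the ongoing time gives (10 + 12 + 1)/3 = 7.7.

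**2. Hand calculation**

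Inputs from the protocol: median DOR 12.5 months and median time to response 1.9 months (Section 1.4, idelalisib), and cut-off 6 months after the last entry (synopsis). Assumed: exponential DOR and uniform accrual over 12 months.

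- λ = ln 2 / 12.5 = 0.05545 per month; true mean 1/λ = 18.0 months.
- C is uniform from 6 − 1.9 = 4.1 to 18 − 1.9 = 16.1 months.
- Proportion ongoing = (e^(−4.1λ) − e^(−16.1λ)) / (12λ) = (0.797 − 0.410)/0.665 = 0.58.
- Counted mean = (1/λ)(1 − 0.58) = 7.5 months against 18.0.
- Counted median solves e^(−λt)(16.1 − t)/12 = 0.5. At t = 7.17 this is 0.672 × 0.744 = 0.500, so 7.2 months against 12.5.

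Simulation of this case with 21 responders (9/17 = 53% of the maximum 40 patients) gives the same figures, and a mean of 4.9 and median of 4.4 months if ongoing responders are dropped.

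**3. Simulation on the protocol's scan schedule**

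Assumed: 10 responders (about one histology group); response found at the first (70%) or second (30%) 84-day scan; exponential DOR with median 12.5 months; progression dated at the next scan; censoring at the last scan; end 6 months after last entry; 40,000 replicates.

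| Accrual (months) | 6 | 12 | 18 | 24 | 36 |
|---|---|---|---|---|---|
| Still in response | 80% | 69% | 60% | 52% | 41% |
| Counted: median | 3.6 | 5.6 | 7.1 | 8.2 | 9.7 |
| Counted: mean | 3.8 | 6.0 | 7.8 | 9.3 | 11.5 |
| Dropped: median | 3.8 | 5.1 | 6.3 | 7.3 | 8.9 |
| Dropped: mean | 3.9 | 5.4 | 6.8 | 8.1 | 10.2 |

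Against 12.5, the counted median is low by 1 − 3.6/12.5 = 71% at one end and 1 − 9.7/12.5 = 22% at the other. With full follow-up on the same scan grid, the average sample median would be 14.8 and the mean 19.4 months, so comparing with 12.5 and 18.0 understates the shortfall. Under the dropped reading at 6 months' accrual, no responder has a completed duration in 11% of trials (0.80^10 = 0.11).

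The Kaplan-Meier 6-month rate in the same data averages 0.73 to 0.74 against a true e^(−6λ) = 0.72.

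**Sensitivity of the counted median**

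- All responses at the first scan: 4.4 to 10.0 months. All at the second: 2.2 to 8.9.
- Up to half of responders scanned only every 6 months: a shift of at most 0.6 months.
- True median 24 months: 3.8 to 12.8.
- End 20 months after last entry, so that every responder can be followed past 12.5 months: 12.9 to 14.0. The dropped median is still only 8.5 to 11.3.

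**The case against.** The strongest reply is deferral. Section 9 says a SAP, due before database lock, will set out censoring for time-to-event variables, DOR is plainly one, and Section 9.10.2 leaves room for a suitable method. This lowers the urgency but does not cure the text. Nothing withdraws the sentence in 8.6.1, it is the only DOR summary the protocol names, and a raw mean and SD have no direct censored form for a later rule to attach to.

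Second, the dropped reading is strained. Section 9 lists missing data and censoring as separate matters, and 8.6.1 asks for the summary in the responders, not in those who have relapsed. That is fair. The case rests on the counted reading; the other matters because the text does not exclude it.

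Third, the size rests on assumptions: accrual, number of responders, exponential shape, another drug's median, and the earliest end that a permissive sentence allows. Other sections continue treatment to progression and follow patients who stop early. With long follow-up and little dropout the counted median is hardly affected. Because progression is dated at scans, the counted mean can then even exceed the population value of 18.0; it stays below the same patients' eventual mean. This all stands as a limit on size. The direction does not depend on it.

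**Conclusion.** The sentence is wrong as written and should be corrected. Followed literally with ongoing responses counted, it gives a mean below the patients' eventual mean whenever any response is ongoing, and a median that is low unless the ongoing responses already exceed it. With ongoing responders dropped, both are low in expectation.

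At the earliest permitted cut-off the counted median is roughly 22% to 71% below an assumed true 12.5 months, for accrual from 36 down to 6 months. These figures illustrate; they do not predict.

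The reach is limited: one arm, no formal claims (Section 9.11), ORR untouched, DOR secondary in Section 9.10.2, and the dates needed for a proper analysis already collected.

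**What to change.** Replace the sentence in Section 8.6.1 with wording such as:

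> DOR will be estimated by the Kaplan-Meier method. Responders without documented progression or death will be censored at their last adequate disease assessment. The number censored and the median with 95% confidence interval, if reached, will be reported by histology and combined.

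Carry this into the SAP, with rules for new anticancer therapy and missed assessments (off-treatment follow-up is only about every 6 months or per standard of care), and state there that an ongoing response is censored and not missing under Section 9.9.

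Useful but optional: median follow-up, landmark rates with numbers at risk where follow-up supports them, and agreement between Sections 2.1 and 9.10 on whether DOR is primary or secondary.

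The cost is wording and standard output. The drawback is that an early cut-off often yields no median: in the 10-responder simulation it is reached in about 22/44/64/79/93% of trials at 6/12/18/24/36 months' accrual, and in 9/18/30/42/64% if the true median is 24 months. Landmarks can also be empty: nobody is at risk at 6 months in 42/1/0/0/0% of trials, or at 12 months in 100/63/11/4/1%. So no landmark should be fixed in advance. A median reported as not reached, with the number censored, is still more informative than a raw median of 3.6 months when 80% are still responding.
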